Diabetes	21 (43)	16 (15)				

ADRs in Multicenter Prospective, Randomized U.S. Trial

•		
	Tacrolimus	Cyclosporine/AZA
	(n=250)	(n=250)
Headache	64%	60%
Insomnia	64%	68%
Tremor	56%	46%
Paresthesia	40%	30%

3) Study interventions

- a) Interventions, administration, and duration
 - i) Subjects will receive the current standard of care for up to 15 days and no longer than 1 year post-transplant. Standard of care is described as a regimen of tacrolimus IR (goal 12 hour trough: 3-10ng/mL) BID ± adjunctive agent ± prednisone. Subjects are randomized to one of the two arms to either receive their standard of care regimen or convert their tacrolimus IR BID to Envarsus QD
 - (1) Both products FDA approved for preventing rejection in kidney transplant and are used as a standard of care for all organ transplants
 - ii) Post-randomization, subjects will be converted to one of the two arms, as shown below, and followed for a total period of six months (primary endpoint), or until a terminal end point is reached.
 - (1) Arm 1: Control-- Tacrolimus IR (goal 12 hour trough: 3-10ng/mL) BID ± adjunctive agent ± prednisone x 6 months
 - (2) Arm 2: Intervention-- Envarsus (goal 24 hour trough: 3-10 ng/mL) daily ± adjunctive agent ± prednisone x 6 months

- (a) Envarsus will be supplied from Veloxis Pharmaceuticals
- b) Neurotoxicity assessment
 - Changes in neurotoxicity comorbidity burden will be assessed at all study visits noted on the Schedule of Evaluations, using the composite score from applying the PGI-I score to tremor, headache, insomnia, and paresthesia.

4) Study Endpoints

- i) Primary outcome- Treatment efficacy, defined difference in change from baseline to six month measure by composite PGI-I in both arms.
- ii) Secondary outcomes
 - (a) Change in the FTM score in patients with self-reported tremor between baseline and six months post-enrollment in both arms
- iii) Exploratory outcomes
 - (1) Safety outcomes of treatment failure rate, defined as acute allograft rejection with a Banff RAI 5 or higher, graft loss, death, adverse events, or severe adverse events at six months post-conversion in both arms.
 - (2) Change in self-reported medication adherence, defined as the IMAB-Q10, between baseline and six months post-conversion in both arms
 - (3) Change in the subject specific quality of life, defined as the SF-12, between baseline and six months post-conversion in both arms

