 - (1) No deviations from or changes to the study protocol should be initiated except when necessary to eliminate immediate hazard to the subject. However, the IRB and Study Sponsor must be informed of this as soon as possible thereafter. It is the PI's responsibility to report SAEs occurring during the study to the IRB, as required and as soon as possible.

10) Study design

- i) Single-center, open-label, randomized comparative trial for a duration of 6 months.
- ii) There will be 15 subjects in each arm, with a total study size of 30 subjects.
- **b)** Allocation: Three random permuted-blocks of ten, with equal arm allocation ratio will be used. In each block, REDCap will be used to ensure 1:1 randomization, with resulting 1:1 allocation in the overall cohort.
- c) Intervention Model: Parallel assignment
- **d)** Masking: This will be an open-label study as masking is not feasible given we are comparing twice-a-day to once-a-day regimen.
- e) Timing of evaluation
 - i) Pre-Randomization Evaluations
 - 1. Baseline
 - Evaluations listed under the baseline visit may be performed up to 14 days prior to randomization. Once the subject has been successfully screened and accepted for randomization, randomization must be completed within 48 hours.
 - ii) Intervention and Evaluations
 - Once the subject has been successfully randomized, study medication will be picked up from IDS by the study team to be dispensed to the subject or study medication will be shipped to the subject by IDS. Study evaluations must take place within the time window indicated on the Schedule of Evaluations (Section 3)
- f) Clinical and laboratory evaluations

i) Schedule of evaluations

Data Collection Schedule

	Baseline	Baseline Days Post-Conversi					on			
Report Form			7±2	14±3	30±5	60±7	90±10	120±10	150±10	180±10
Informed Consen	t Obtained ^{vi}	Х								
Randomization		Х								
Review of Inclusion	on and Exclusion Criteria	Х								
Medical History		Х								
Liver Transplant F	Recipient	Х								
Review of Medica	ations and Dosing	Х								Х
Clinical assessment* Adverse events, rejection, graft loss, death						х			х	
	PGI-I, IMAB-Q 10, MSVT, MoCA, and SF- 12, MMSE ^v	х								х
	Fahn-Tolosa-Marin ^{iv}	Х								Х
Laboratory	CBC and Chem-7 ⁱ	0	0	0	0	0	0	0	0	0
Assessments	LFTs ⁱⁱ	0	0	0	0	0	0	0	0	0
	Tacrolimus CO ⁱⁱⁱ	0	0	0	0	0	0	0	0	0
End of Study										Х

X=required; 0=optional: data will be collected if performed as standard of care Footnotes:

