 - (1) Opportunistic infections will be defined as outlined in Appendix F
- v) Intervention Discontinuation Evaluations: At the scheduled time of intervention discontinuation (EOT, last date of study), the following evaluations must be completed: clinical assessment, CBC, CHEM-7, LFTs, Tacrolimus CO. In case of subject withdrawal from study, the patient will return to standard of care medications and request to continue with final assessment using PGI-I, IMAB-Q 10, MSVT, MoCA, SF-12, MMSE, and FTM (if applicable) will be discussed with a qualified team member.

12) Data Management

- a) Data management will be overseen and data analysis will be independently reviewed by an Investigator on the study who has no related financial interest. This member will serve as independent monitor to oversee data collection and management, and to verify the integrity of data and interpretation of study results. Data reports, including patient recruitment and randomization numbers, clinical outcomes (acute rejections, infections and hospitalizations), AEs and SAEs will be reviewed quarterly.
- b) Dichotomous data will be analyzed using Chi Square or Fischer Exact, when appropriate, and continuous data points will be analyzed using Student's t-test or Mann Whitney U, for parametric and nonparametric data, respectively.
- c) Sample size estimation for the primary outcome
 - i) The proposed sample size (n=30) would be able to demonstrate a mean difference in neurologic toxicity burden, using the Patient Global Impression of Improvement (PGI-I) rating of 20 ± 15 with greater than 80% power using a two-tailed t-test with an alpha set at 0.05. Based on reported neurologic toxicities from the literature (headache 64%, insomnia 64%, tremor 56%, paresthesia 40%), a mean score of 45 is expected at baseline. Using the independent samples t-test comparing two groups with a two-sided significance level of

0.05, a sample size of 14 subjects per group would be required to obtain a power of at least 0.8 if the two groups have a mean of 25 ± 15 neurologic toxicity burden in the Envarsus cohort at the conclusion of the study and mean of 45 ± 20 neurologic toxicity burden at baseline and follow up in the tacrolimus IR group. Estimating a 10% drop out rate, we propose a sample size of 15 subjects per group. This sample size will provide adequate power to show a statistical and clinical difference in the neurologic toxicity burden between the two groups.

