- i) An adverse event (AE) is any untoward medical occurrence (i.e., any unfavorable and unintended sign [including abnormal laboratory findings], symptom or disease) in a subject or clinical investigation subject after providing written informed consent for participation in the study. Therefore, an AE may or may not be temporally or causally associated with the use of a medicinal (investigational) product. The occurrence of adverse events should be sought by non-directive questioning of the subject at each visit during the study. Adverse events also may be detected when they are volunteered by the subject during or between visits or through physical examination, laboratory test, or other assessments. Abnormal laboratory values or test results constitute adverse events only if they fulfill at least one of the following criteria:
 - (1) they induce clinical signs or symptoms,
 - (2) they are considered clinically significant,
 - (3) they require therapy
- ii) Clinically significant abnormal laboratory values or test results should be identified through a review of values outside of normal ranges/clinically notable ranges, significant changes from baseline or the previous visit, or values which are considered to be non-typical in subject with underlying disease. Investigators have the responsibility for managing the safety of individual subject and identifying adverse events. Adverse events should be recorded in the Adverse Events CRF with them accompanied by the following information:
 - (1) severity of adverse events will be determined using the grading system outlined in the NCI Common Terminology Criteria for Adverse Events Version 4.03 (CTCAE), as it best fits the diagnostic terminology used in naming the event at the site clinical level.
 - (2) possibility of relationship to the study treatment (no/yes)
 - (3) its duration (start and end dates) or if the event is ongoing an outcome of not recovered or not resolved should be reported.
 - (4) whether it constitutes a serious adverse event (SAE), if so report date should be provided
 - (5) action taken regarding study treatment
 - (6) whether other medication or therapies have been taken (concomitant medication/non-drug therapy)
 - (7) its outcome (not recovered/not resolved; recovered/resolved; recovering/resolving, recovered/resolved with sequelae; fatal; or unknown)
- iii) An SAE is any adverse event which meets any one of the following criteria:

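### For subjects who withdraw, Section 11(v) does not name the clinical assessment among the evaluations to seek, and the available text sets no active capture of rejection, graft loss, death and adverse events to day 180 in both arms

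*Combined protocol and SAP*

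**What the plan says.** Section 11(v) has two consecutive rules. At the scheduled end of the intervention, "the following evaluations must be completed: clinical assessment, CBC, CHEM-7, LFTs, Tacrolimus CO". For leavers the next sentence begins "In case of subject withdrawal from study, the patient will return to standard of care medications" and goes on to name what is to be sought: "request to continue with final assessment using PGI-I, IMAB-Q 10, MSVT, MoCA, SF-12, MMSE, and FTM (if applicable) will be discussed". The schedule in Section 10(f)(i) defines the clinical assessment row as "Adverse events, rejection, graft loss, death".

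These events feed three uses:

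- Section 4(iii)(1) plans "Safety outcomes of treatment failure rate, defined as acute allograft rejection with a Banff RAI 5 or higher, graft loss, death", and the definition then goes on to include adverse events and severe adverse events, at six months in both arms.
- Section 1(c)(vi) plans time-to-event analyses of death, biopsy-proven rejection and graft loss.
- Section 13(a)(2) plans a safety review of 16 subjects, with between-arm differences above 20% in rejection, grade 3 or higher infection, or graft loss as example triggers.

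For binary data Section 12(b) says "Dichotomous data will be analyzed using Chi Square or Fischer Exact, when appropriate".

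**The concern.** The protocol foresees approaching leavers for more data and lists which data. The safety events are not on the list, although the sentence before makes them mandatory at the scheduled end. A site that follows the list literally could obtain a withdrawn subject's MoCA score and not record a later rejection.

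If an event after departure goes unrecorded and the subject stays in the denominator, a crude six-month proportion is too low. If leaving differs between arms, which is possible in an open-label trial, the comparison shifts as well. Follow-up that was never collected cannot be restored by the analysis.

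**Working it through.** **Provisions that might fill the gap**

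| Place | What it provides | What it leaves open for leavers |
|---|---|---|
| 3(a)(ii) | Six months of follow-up, or to a terminal end point | Source of data after withdrawal |
| 11(i)(2) | Clinical assessment of all subjects at scheduled times | Whether the schedule continues after withdrawal |
| 12(a) | "clinical outcomes (acute rejections, infections and hospitalizations), AEs and SAEs will be reviewed quarterly" | Reviews data already held; does not collect |
| 12(d) | Intention-to-treat; a general effort to limit missing data | Procedure |
| 13(b)(i) | Questioning at visits; "Adverse events also may be detected when they are volunteered by the subject during or between visits" | Leavers have no study visits |
| 13(c), 13(d) | Reports to the supplier for Envarsus subjects: deaths and related, unexpected SAEs to 72 hours after stopping; then related SAEs if the investigator learns of them | Passive, one arm only, not to day 180 |
| 14(a) | Reasons to stop the intervention | Any later follow-up |

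The general rules show intent to follow everyone. None gives a source and an end date for these events, in both arms, after withdrawal.

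**Size**

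The plan gives no figure for this loss, so there is none to reproduce. The one planning input it supplies is 10% dropout (Section 12(c)): 0.10 × 30 = 3 subjects. One missed event among 15 is 1/15 = 6.7 points.

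Inputs for an illustration with rejection:

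- One-year rejection 31% (Section 2(a)). This comes from patients taken off tacrolimus and may be too high here.
- Assumptions of this review: constant hazard; 10% of event-free subjects leave at month 2; no capture afterwards; leavers counted as non-events; hazard after leaving multiplied by h = 1, 2 or 3.

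Steps:

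1. λ = −ln(1 − 0.31)/12 = 0.0309 per month. Six-month rate = 1 − exp(−6λ) = 16.9%.
2. Missed probability per subject = exp(−2λ) × 0.10 × [1 − exp(−4hλ)]. For h = 1 this is 0.940 × 0.10 × 0.1163 = 0.0109.
3. Missed per arm = 15 × that probability.
4. Crude observed rate = true rate − missed probability.
5. An estimate that censors leavers at month 2 recovers 16.9% for every h.

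| h | Missed per arm | True rate | Crude rate | Crude shortfall (points) | Bias with censoring (points) |
|---|---|---|---|---|---|
| 1 | 0.16 | 16.9% | 15.8% | 1.1 | 0 |
| 2 | 0.31 | 17.9% | 15.8% | 2.1 | −1.0 |
| 3 | 0.44 | 18.8% | 15.8% | 2.9 | −1.8 |

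Further results:

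- Chance that no rejection is missed among all 30 (h = 1): (1 − 0.0109)^30 = 72%.
- With 20% leaving one arm and none the other (assumed), the crude comparison shifts by twice the shortfall before rounding: 2.2, 4.1 or 5.8 points.
- With assumed six-month rates of 10% to 20% and h from 1 to 3, missed events per arm run from 0.10 to 0.50 and the crude shortfall from 0.7 to 3.3 points.

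**The case against.** The strongest reply is that the lists in Section 11(v) are not exhaustive. The scheduled-end list omits the PGI-I, yet the schedule requires it at day 180 and nobody would conclude that the primary endpoint goes uncollected. The withdrawal list can be read as naming what needs the subject's active cooperation, with the general follow-up rules still in force. At a single centre, with biopsies done when clinically warranted, staff may see many events in routine records anyway. This stands as a fair reading, and it is why the point is about wording that should be made explicit. It does not supply a data source or an end date for leavers.

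Four stronger readings are tempting, and the documents do not support them.

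- *That the protocol abandons safety follow-up after withdrawal.* The general rules point the other way, Section 13(c) and (d) does reach some events after the drug is stopped, and the missing consent pages and footnote could hold a provision.
- *That everyone who stops study drug is lost.* Stopping the intervention (Section 14) and withdrawing from the study (Section 11(v)) are worded separately. Those who only stop drug can be read as staying on schedule, although this is not stated.
- *That the treatment-failure rate is materially wrong.* That composite also counts any adverse event, so a subject stopped for a grade 3 event has already failed before leaving. It is affected less than rejection alone.
- *That the 16-subject review is compromised.* Its thresholds are examples for a monitor's judgement. Taken literally it covers subjects who completed follow-up, so leavers would not be seen at all. Only if they stay in the denominator could missed events move the rejection difference across 20 points. With 8 per arm and equal true rates, the exact probability under the illustration is 5.1% (9.0% and 12.1% for h = 2 and 3).

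**Conclusion.** The point holds as a minor gap and a cheap improvement. The withdrawal provision does not name the safety assessment, and no available text sets active capture to day 180 in both arms after withdrawal. The primary endpoint and its power are untouched, since the PGI-I is on the list sought from leavers.

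In the base illustration the expected loss is a fraction of one rejection per arm, and the crude rate falls by about one point. Rejection, death and graft loss are named for time-to-event analysis, where censoring leavers gives no bias unless withdrawal is related to risk. The figures rest on a borrowed 31% rate and on assumed timing, hazard and handling of leavers. They show scale and do not predict what this trial will lose. Confidence is medium because of the missing pages.

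**What to change.** - In Section 11(v), add the clinical assessment (adverse events, rejection, graft loss, death) to the evaluations sought on withdrawal.
- In Section 14, state that stopping study drug is not withdrawal from the study.
- State that, unless consent to record review is withdrawn, rejection, graft loss, death and SAEs are collected from transplant-centre records to day 180 for every randomised subject in both arms, and are analysed by randomised arm.
- In Section 13(a)(2), state that early leavers are included in the 16-subject review.

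The cost is protocol and consent wording plus about three chart reviews at the planned dropout. Adverse events taken from records will be less complete than those asked about at visits, and subjects who refuse record review still cannot be followed.

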Title:

The effect of conversion to once-daily Envarsus® on the neurologic toxicity burden in liver transplant recipients

Institution:

Medical University of South Carolina

Principal Investigators:

[name]

Office: [contact] [contact] Email: [contact]

1) Study Objectives

- a) Primary objective
 - i) Estimate the change from baseline to six months in neurotoxicity burden measured by a composite Patient Global Impression of Improvement (PGI-I) (Appendix B) score in patients converted to Envarsus daily ± adjunctive agent ± prednisone versus patients maintained on a standard therapy of Tacrolimus IR BID ± adjunctive agent ± prednisone

b) Secondary objectives

i) Estimate the change in the mean Fahn-Tolosa-Marin (FTM) score in patients with selfreported tremor from baseline to 6 months after enrollment

c) Exploratory Outcomes

- Examine subject specific change of self-reported adherence using the IMAB-Q 10 (Appendix C) at the time of the conversion versus six months post-conversion, compared between the two arms
- **ii)** Examine subject specific change in quality of life, using the SF-12 at the time of conversion versus six months post-conversion, compared between the two arms
- **iii)** Examine subject specific change in memory, using the Medical Symptom Validity Test, at the time of conversion versus six months post-conversion, compared between the two arms
- **iv)** Examine subject specific change in cognition, using the MoCA (Appendix E), at the time of conversion versus six months post-conversion, compared between the two arms
- v) Examine subject specific change in cognition, using the MMSE, at the time of conversion versus six months post-conversion, compared between the two arms
- vi) Measure and compare time-to-event analysis of secondary objective between the two arms
 - (1) Patient death (time to event analysis)
 - (2) Biopsy proven acute rejection (Banff RAI ≥ 5, time to event analysis)
 - (3) Graft loss (time to event analysis)
- vii) Compare rates of adverse events and severe adverse events between the two arms
- viii) Examine subject specific change in renal function, using the 4 variable MDRD, at the time of conversion versus six months post-conversion, compared between the two arms

2) Background

a) Rationale

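### The primary outcome is change from baseline, but the 14 per group comes from six-month scores; the power of an unadjusted change test is unsupported, and baseline-adjusted ANCOVA would be more efficient with data already collected

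*Combined protocol and SAP*

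**What the plan says.** - **Objective and outcome.** Section 1 a) sets the primary objective as "Estimate the change from baseline to six months in neurotoxicity burden", compared between arms. Section 4 i) gives the primary outcome as "defined difference in change from baseline to six month measure by composite PGI-I in both arms".
- **Test.** Section 12 b) covers all continuous data with Student's "t-test or Mann Whitney U, for parametric and nonparametric data, respectively". It names no covariate and does not single out the primary outcome.
- **Sample size.** Section 12 c), which is headed as the calculation for the primary outcome, opens with a difference in "rating of 20 ± 15 with greater than 80% power using a two-tailed t-test". It then derives 14 per group from an independent-samples t-test on a "mean of 25 ± 15 neurologic toxicity burden in the Envarsus cohort at the conclusion of the study" and a "mean of 45 ± 20 neurologic toxicity burden at baseline and follow up in the tacrolimus IR group". The expected baseline mean is 45.
- **Dropout.** "Estimating a 10% drop out rate, we propose a sample size of 15 subjects per group".
- **Baseline.** The schedule in Section 10 f) requires the PGI-I at baseline and at day 180. Section 10 e) places it before allocation: "Evaluations listed under the baseline visit may be performed up to 14 days prior to randomization".
- **Scale.** Appendix B shows four items with seven response categories each, and no rule for combining them into a composite.

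**The concern.** The variance of a change score depends on the correlation between baseline and six months. The variance of a six-month score does not. A sample size worked out for one does not carry over to the other unless that correlation, or the SD of change, is known, and the plan gives neither. The expected effect is the same either way: with both arms starting at 45, the difference in change is also 20. Only the SD is in doubt.

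At stake is power in a 30-patient trial with little slack. If the correlation is modest, subtracting baseline adds noise and an unadjusted change test falls well short of 80%. The baseline score is measured before randomisation, so it could be used as a covariate at almost no cost, and the plan does not use it. This is a matter of efficiency and of an unsupported power statement. It does not threaten the validity of the test.

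**Working it through.** **Inputs from Section 12 c).** Difference 20; six-month SDs 15 (Envarsus) and 20 (tacrolimus IR); two-sided alpha 0.05; 14 per group, 15 with dropout. The only stated baseline SD is 20, given for the tacrolimus IR group. **Assumed:** baseline SD 20 in both arms, as randomisation would suggest; correlation r varied, because none is stated; normal data.

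**1. Reproduce the plan's figure.** Root-mean-square SD of the six-month scores = √((15² + 20²)/2) = √312.5 = 17.68. The noncentral t gives power 0.790, 0.822 and 0.849 at 13, 14 and 15 per arm. The smallest n reaching 0.80 is therefore 14, as stated. An SD of 15 in both arms would give 10 per group, and 20 in both would give 17. The stated 14 is the size for comparing six-month scores.

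**2. Unadjusted change.** Var(change) = SD₀² + SD₆² − 2·r·SD₀·SD₆.
- Tacrolimus IR: 400 + 400 − 800r = 800 − 800r
- Envarsus: 400 + 225 − 600r = 625 − 600r
- Mean of the two: 712.5 − 700r

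The root-mean-square SD is √712.5 = 26.7 at r = 0, √502.5 = 22.4 at r = 0.3, √362.5 = 19.0 at r = 0.5 and √222.5 = 14.9 at r = 0.7. Power at 14 per arm is 0.48, 0.62, 0.76 and 0.93 respectively. Change is noisier than the six-month score until 712.5 − 700r = 312.5, that is r = 0.57.

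**3. ANCOVA of the six-month score on arm and baseline.** The pooled baseline slope is (r + 0.75r)/2 = 0.875r. Residual variance is 312.5 − (0.875r)²·400 = 312.5 − 306.25r². One degree of freedom is lost. The residual SD is 17.7, 16.9, 15.4 and 12.7 at r = 0, 0.3, 0.5 and 0.7. Power at 14 per arm, confirmed by simulation, is 0.80, 0.84, 0.90 and 0.97.

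**4. Across the likely numbers of completers.** A 10% loss from 30 leaves 27, so 14 and 13.

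| Evaluable per arm | Change, r = 0.3 / 0.5 | r needed for 80% (change) | Largest SD of change for 80% | ANCOVA, r = 0 / 0.3 / 0.5 |
|---|---|---|---|---|
| 15 | 0.66 / 0.79 | 0.51 | 18.9 | 0.83 / 0.87 / 0.92 |
| 14 | 0.62 / 0.76 | 0.55 | 18.2 | 0.80 / 0.84 / 0.90 |
| 14 and 13 | about 0.61 / 0.75 | about 0.56 | 17.8 | 0.79 / 0.82 / 0.89 |
| 13 | 0.59 / 0.73 | 0.58 | 17.5 | 0.77 / 0.81 / 0.87 |

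With 14 and 13 completers, ANCOVA reaches 0.80 near r = 0.2.

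**5. The other reading of 20 ± 15.** If 15 is the SD of change, the change test has power 0.90, 0.92 and 0.94 at 13, 14 and 15 per arm. Setting 712.5 − 700r = 225 gives r = 0.70, a value the plan does not state. At that correlation ANCOVA gives 0.96, 0.97 and 0.98.

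**6. Type I error.** Simulated at 14 per arm with r = 0.3 and 0.5, it is 0.050 to 0.051 for both analyses. With 14 and 13 it stays between 0.048 and 0.054.

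**The case against.** **The plan may mean a six-month comparison.** Section 12 c) never uses the word change, its t-test inputs are end-of-study scores, and for those the power claim is correct. Section 12 b) is a generic sentence, so a test on change is an inference. This is fair as far as it goes. But Section 12 c) is headed as the calculation for the primary outcome, and Sections 1 and 4 define that outcome as change. The two need reconciling on either reading.

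**ANCOVA is not always the most powerful choice.** Against a t-test on six-month scores alone it loses up to about 2 points when r is below about 0.2 (0.80 against 0.82 at 14 per arm with r = 0), and at r = 0.3 it gains less than 2 points. This stands, but the six-month-only test is not the declared outcome, and the loss is small beside the gain at higher r.

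**The comparison depends on an assumed baseline SD.** With 15 in both arms, ANCOVA and the change test tie at r = 0.7 and 14 per arm (both about 0.97). With 15 in the Envarsus arm only, which randomisation does not imply, the r needed for 80% at 14 per arm falls from 0.55 to 0.47. The size of the shortfall is therefore conditional, although ANCOVA loses nothing material in these cases.

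**20 ± 15 may be the SD of change.** Then there is no shortfall. That reading needs only 10 per group, so it does not explain the stated 14.

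**The scale is undefined.** Without a scoring rule for the composite, all these figures, the plan's own included, rest on a scale the documents do not describe. This stands and has to be settled first.

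**Conclusion.** The concern holds. The stated 14 per group is arithmetically right for six-month scores, and the plan gives nothing that carries it over to change. Taking the plan's SDs with a baseline SD of 20 in both arms, an unadjusted change test reaches 80% only if r is at least about 0.51 to 0.58, depending on whether 15 or 13 per arm are evaluable. The plan offers no way to place r. The PGI-I items ask for a comparison with the time before transplant, so no particular value should be presumed. Power could lie above or below 80%: it is unsupported, not shown to be too low.

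Under the same assumptions ANCOVA had higher power than the change test at every correlation examined from 0 to 0.7. It assures 80% for every r of 0 or more only with at least 14 per arm. At the expected 27 completers it needs r of about 0.2. All figures are for t-type tests on normal data and do not describe the rank test. This should be fixed, as a gap in the power case and a loss of efficiency in the primary analysis.

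**What to change.** 1. In Section 12, name as the primary analysis an ANCOVA of the six-month composite on arm with the baseline composite as covariate. Report the adjusted mean difference with its 95% confidence interval. The adjusted difference is the same whether the response is the six-month score or the change, so Sections 1 and 4 can stand.
2. State how the four PGI-I items are scored and combined.
3. Restate power on that scale over a range of r, for 13 to 15 evaluable per arm, and say what the ± 15 in the opening sentence refers to.
4. If unadjusted change is kept instead, state the SD of change, or r, that supports 80%.

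The role of the Mann-Whitney test can remain the sponsor's choice; this change does not depend on it. The cost is a few lines in Section 12 and one degree of freedom, with no new data, visits or patients. Step 3 cannot be done until step 2 is settled.

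### The sample-size inputs in Section 12 c) do not match the PGI-I composite or the change endpoint, so power above 80% is not shown

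*Combined protocol and SAP*

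**What the plan says.** **Endpoint.** The primary objective (Section 1 a) is to "Estimate the change from baseline to six months in neurotoxicity burden measured by a composite Patient Global Impression of Improvement (PGI-I") score, compared between arms. Section 4 i) gives the primary outcome as "defined difference in change from baseline to six month measure by composite PGI-I in both arms". Section 3 b) builds the composite from PGI-I ratings of tremor, headache, insomnia and paresthesia. Appendix B shows four items, each with seven verbal categories. The documents give no numeric codes, combining rule, direction or range.

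**Sample size (Section 12 c).** The section first describes a mean difference "using the Patient Global Impression of Improvement (PGI-I) rating of 20 ± 15 with greater than 80% power" for n = 30. It then takes a baseline value from literature rates: "headache 64%, insomnia 64%, tremor 56%, paresthesia 40%), a mean score of 45 is expected at baseline". The calculation itself is an independent-samples t-test at two-sided 0.05 with 14 per group. It compares a "mean of 25 ± 15 neurologic toxicity burden in the Envarsus cohort at the conclusion of the study" with a "mean of 45 ± 20 neurologic toxicity burden at baseline and follow up in the tacrolimus IR group". On dropout it says: "Estimating a 10% drop out rate, we propose a sample size of 15 subjects per group". It concludes: "This sample size will provide adequate power to show a statistical and clinical difference in the neurologic toxicity burden".

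**The concern.** Section 12 c) is the only justification for 30 subjects, and three links between its inputs and the primary endpoint are missing.

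- **Scale.** The burden is said to be measured by the PGI-I composite, but 45, 25, 15 and 20 look too large for four seven-category items.
- **Source.** The percentages are shares of patients who have a symptom. No rule turns them into a mean score.
- **Spread.** The endpoint is a change, but the ± values are attached to levels at a time point. The headline ± 15 also differs from the 15 and 20 used in the calculation.

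As it stands, a reader cannot tell what between-arm difference in the composite the trial can detect, or whether that difference would matter to patients. The plan nevertheless claims adequate power for a clinical difference.

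**Working it through.** **1. Reproducing the plan's figure.** Inputs from Section 12 c): difference 45 − 25 = 20, SDs 20 and 15, two-sided alpha 0.05, equal arms. The pooled SD is √((20² + 15²)/2) = 17.68. Two-sample t-test power from the noncentral t distribution:

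| Evaluable per arm | Power |
|---|---|
| 13 | 0.790 |
| 14 | 0.822 |
| 15 | 0.849 |

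So 14 is the smallest number reaching 0.80, as the plan says.

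**2. Scale.** With consecutive-integer coding, a sum of four seven-category items spans 4 × (7 − 1) = 24 points.

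- The sum runs 4 to 28 (items coded 1 to 7), 0 to 24 (0 to 6) or −12 to +12 (−3 to +3). A mean of 45 is outside all three.
- A mean of 25 is possible only on 4 to 28. There the SD is at most √((25 − 4)(28 − 25)) = √63 = 7.9, not 15.
- On any 24-point range the SD is at most 24/2 = 12 (about 12.5 as a sample SD with 14 subjects), below both 15 and 20.
- An item mean cannot exceed 7.
- On a 0 to 100 rescaling, 45 and 25 are possible, and 20 points would equal 0.20 × 24 = 4.8 raw points. The plan states no such rescaling.

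**3. Source of 45.** The four rates match the tacrolimus column of the adverse-reaction table in Section 2. Their simple average is (64 + 64 + 56 + 40)/4 = 56.

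**4. Spread.** If Envarsus also starts at 45, the 20 points fit a difference in change: 0 for tacrolimus IR against −20. The SD of that change is the missing input. At 14 per arm with a 20-point difference:

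| SD of change, both arms | Power | Per arm for 80% |
|---|---|---|
| 15 | 0.92 | 10 |
| 20 | 0.72 | 17 |

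The largest common SD of change that keeps 80% power is 18.2 at 14 per arm and 17.5 at 13.

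Suppose instead that the ± values are SDs of scores. Assume a baseline SD of 20 in both arms, since randomised arms share one expected baseline distribution, and a baseline-to-six-month correlation r, which the plan does not give. Then the SD of change is √(800 − 800r) for tacrolimus IR and √(625 − 600r) for Envarsus:

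| Assumed r | SD of change, IR / Envarsus | Power at 14 per arm |
|---|---|---|
| 0.3 | 23.7 / 21.1 | 0.62 |
| 0.5 | 20.0 / 18.0 | 0.76 |
| 0.7 | 15.5 / 14.3 | 0.93 |

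Power reaches 80% at r of about 0.55.

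**5. Dropout.** 14/0.9 = 15.6, which rounds up to 16, not 15. Conversely, 15 × 0.9 = 13.5 per arm, or 27 in total. On the plan's own inputs, a 13/14 split gives power 0.80 to 0.81, depending on which arm is smaller, and 13 in each arm gives 0.79.

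**6. What holds on any scale.** For a t-test on change, 80% power corresponds to a between-arm difference of 1.10 SD of change at 14 per arm (20/18.2) and 1.15 SD at 13 (20/17.5).

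**The case against.** **No scale is documented, so none is violated.** Appendix B is laid out as a data-capture form, and a form showing only labels does not prove that no coding exists. On a 0 to 100 scale, 45 ± 20 and 25 ± 15 are unremarkable. This stands in part: a reader might infer that the inputs are impossible, but the documents show only that no plain sum or mean can produce them. A rescaling that would rescue them still has to be stated.

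**The calculation compares six-month scores.** With equal expected baselines, the six-month difference and the difference in change target the same 20 points, and for a six-month comparison the 0.82 stands on the plan's inputs. That is fair, but Sections 1 and 4 define the outcome as change, and the comparison would still need a scale that admits 45 and 25.

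**Withdrawal need not mean a missing outcome.** Section 11 v) provides for asking withdrawn subjects to complete the final PGI-I, and Section 12 d) includes all subjects by intention to treat. This stands: the dropout shortfall is small and may not occur.

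**The trial aims to estimate, with 30 subjects at one centre.** True, but the plan also makes an explicit claim of power for a clinical difference, and that claim needs support.

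**Conclusion.** The stated power above 80% is not supported for the primary endpoint as documented. The inputs cannot come from any plain sum or mean of the Appendix B items, 45 does not follow from the cited rates, and the ± values are not identified as SDs of change.

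A reader might go further and conclude that the trial is underpowered. The documents do not support that. Taking 20 points at face value with 14 per arm, the plan's two ± values give 0.72 and 0.92 if read as common SDs of change. Read as SDs of scores, they give 0.62 to 0.93 for r from 0.3 to 0.7. Power may lie on either side of 80%. The r values and the common baseline SD of 20 are assumptions made here. The scale results assume consecutive-integer item codes.

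**What to change.** In Section 12 c):

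1. State the item coding, composite formula, direction and range. The Appendix B items ask for a comparison with the time before transplant, so also say what a baseline burden means on this score.
2. Replace 45, 25 and their ± values with values on that scale, including a justified SD of change (or an SD plus a correlation). If the symptom rates are kept as the source, show how they lead to the baseline mean. Use one set of SDs throughout.
3. Replace the power claims with a detectable difference at the evaluable number.

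Possible wording, with brackets for the sponsor to complete:

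> The composite is the [sum/mean/rescaled score] of the four item scores, coded [ ] to [ ], range [ ], higher values meaning [ ]. With 14 evaluable subjects per arm, a two-sided 0.05 t-test has 80% power for a between-arm difference in change of 1.10 SD of change (1.15 SD with 13 per arm). For an SD of change of [value, source] this is [ ] points, which [is/is not] considered clinically meaningful.

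The multiples apply to the t-test; Section 12 b) also allows Mann-Whitney, for which they would need rechecking.

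The cost is a reworded Section 12 c) and one scoring line. The restatement needs no more patients; whether 30 subjects are enough stays open until the SD of change is supplied. The downside is a power statement that is conditional and may be less favourable.
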